The SEADL scale will be used as a means of assessing the subject's ability to perform daily activities. The Schwab England Activities of Daily Living (SEADL) scale was developed by Schwab and England in 1957 and consists of ten items intended to evaluate the daily life activities of a patient. The SEADL is composed of two sections: the first is a self-report questionnaire in which patients grade their own daily life activities, such as dressing, using the toilet, resting, eating, and social activities (subjective assessment), and the second is an assessment of motor functions, such as postural balance, speaking, rigidity, and tremors, conducted by a clinician (objective assessment). It is a percentage

scale divided into deciles, and the results are reported between 0% (bedridden) and 100% (healthy). It is administered to the subject by a clinician and takes approximately 5 – 10 minutes to complete, as reported in [Table 7](#).

Unified Parkinson's Disease Rating Scale (UPDRS) (Secondary Endpoint)

The Unified Parkinson's Disease Rating Scale (UPDRS)¹⁷ is an Investigator-used rating tool to follow the longitudinal course of Parkinson's disease. The UPDRS assessment will be performed by an approved, trained rater. To be qualified by the Sponsor and the rater vendor, all raters must have participated in the Rater Training and have a current, valid Rater Certificate.

The UPDRS is made up of the following sections:

- Part I – Mentation, Behavior, and Mood
- *Part II – Activities of Daily Living
- Part III – Motor Examination
- Part IV – Complications of Therapy (including dyskinesias)
- Part V – Modified Hoehn and Yahr Staging

* Only Part II will be administered in this study.

It is administered to the subject by a clinician and takes approximately 10 minutes to complete, as reported in [Table 7](#).

Clinical Global Impression of Severity (CGI-S) and Clinical Global Impression of Change (CGI-C) (Secondary Endpoint)

The CGI-S is a clinician's rating of disease severity. The CGI-S rates severity of illness on a 7-point scale, using a range of responses from 1 (normal) through to 7 (the most severely ill). This rating is based upon observed and reported symptoms, behavior, and function in the past 7 days. The CGI-C rates improvement by 7 categories: very much improved, much improved, minimally improved, no change, minimally worse, much worse, very much worse. These assessments are administered to the subject by a

clinician. The CGI-S takes approximately 40 to 60 minutes to complete and the CGI-C takes approximately 1 minute to complete, as reported in [Table 7](#).

PSP-Quality of Life (PSP-QoL)¹⁸ (Secondary Endpoint)

The PSP-QoL is a validated patient-reported outcome measure, specifically designed to assess the quality of life of patients with PSP. There are 45 items and two subscales: physical and mental impact. Items are scored from 0 (no problem) to 4 (extreme problems). The total subscale sum scores are linearly converted into a 0 to 100 scale. The PSP-QoL, with a 4-week time frame, can be completed by the patients or study partners. The PSP-QoL form includes a visual analog scale (VAS) about the patient's satisfaction with overall life. It takes 30 minutes to complete. The PSP-QoL was developed specifically for PSP and displays good psychometric properties. A panel of experts in movement disorders determined that content validity was good. Internal construct validity was verified through a moderate correlation between the two subscales. Convergent and discriminant validity was supported by correlations between the PSP-QoL subscales and other measures (EuroQol-5D [EQ-5D] and the Hospital Anxiety and Depression Scale), with no differences by gender. PSP-QoL is administered to the subject by a clinician and takes approximately 30 minutes to complete, as reported in [Table 7](#).

Repeatable Battery for Assessment of Neuropsychological Status (RBANS)¹⁹ (Exploratory Endpoint)

The RBANS is a 25-minute, standardized neurocognitive battery with North American population-based normative data. The RBANS measures five neurocognitive domains, with age-based scaling. Twelve subtests measure cognitive decline or improvement across the following domains:

1. Immediate Memory – List Learning and Story Memory,
2. Visuospatial/Constructional – Figure Copy and Line Orientation,
3. Language – Picture naming and Semantic Fluency,
4. Attention – Digit Span and Coding, and

5. Delayed Memory – List Recall, List Recognition, Story Memory, and Figure Recall.

The RBANS has been shown to be effective at both detecting and characterizing dementia of different etiologies. The RBANS has been translated into over 25 different languages, with extensive clinical validity data from a wide variety of geographic regions. It is administered to the subject by a clinician and takes approximately 25 minutes to complete, as reported in [Table 7](#).

Color Trails Test (CTT) (Parts 1 and 2)²⁰ (Exploratory Endpoint)

The Color Trails Test (CTT) (Parts 1 and 2) involves numbered circles that are printed with vivid pink or yellow backgrounds that are perceptible to color-blind individuals. For Part 1, the respondent uses a pencil to rapidly connect circles numbered 1 – 25 in sequence. For Part 2, the respondent rapidly connects numbered circles in sequence, but alternates between pink and yellow. The length of time to complete each trial is recorded, along with qualitative features of performance indicative of brain dysfunction, such as near-misses, prompts, number sequence errors, and color sequence errors. The clinician administering this test will need a stopwatch to record the length of time for the completion of each part. It is administered to the subject by a clinician and takes approximately 5 – 10 minutes to complete, as reported in [Table 7](#).

Letter Fluency Test (LFT)²¹ (Exploratory Endpoint)

This is a phonemic fluency task, requiring subjects to generate as many words as they can that start with a given letter over a 60 second interval. This study will employ two trials per administration, involving different letters. The score is the total number of correct words generated over the two trials. It will be administered to the subject by a clinician and will take approximately 1 minute for each of the two trials to complete, as reported in [Table 7](#).

Natural History and Neuroprotection in Parkinsons Plus Syndromes-Parkinson Plus Scale (NNIPPS-PPS)²² (Exploratory Endpoint)

The NNIPPS-PPS is a validated rating scale used to assess disease severity and progression in patients with PSP and MSA. The NNIPPS-PPS contains 83 items, comprised of 11 domains: functional disability (ADLs), mental function (cognition, mood, and behavior), motor disability (rigidity and bradykinesia), tremor, oculomotor function, cerebellar signs, pyramidal signs, dysautonomia, bulbar/pseudobulbar symptoms, myoclonus, and dystonia. Responses are graded according to their severity. It is administered by a clinician and takes approximately 30 – 45 minutes to complete, as reported in [Table 7](#).

The NNIPPS-PPS will not be administered in Japan.

Patient Global Impression of Change (PGI-C)²³ (Exploratory Endpoint)

Subjects will evaluate the change in their PSP-related symptoms since initiation of study drug by choosing one of seven responses. The PGI-C is a 7-point response scale. The subject will be asked by the Investigator or qualified designee to rate their change in status using the following 7-point scale:

1 = Very much improved, 2 = Much improved, 3 = Minimally improved, 4 = No change, 5 = Minimally worse, 6 = Much worse, 7 = Very much worse.

The responses of "Very much improved," "Much improved," "Minimally improved" and "No change" on the PGI-C will be used to define responders. It is administered to the subject by a clinician and takes approximately 1 – 2 minutes to complete, as reported in [Table 7](#).

EuroQuality of Life (EQ-5D)²⁴ (Exploratory Endpoint)

The EQ-5D contains a health state descriptive part comprising five items, scored from 1 (no problems or symptoms) to 3 (serious problems or symptoms); a question about change in health state in the preceding 12 months, and a VAS to evaluate current health

state (from 0, worst imaginable, to 100, best imaginable). The descriptive profile can be converted into a value (EQ-Index) which ranges from 0 (death) to 1 (perfect health), with negative values indicating health states considered worse than death. It is administered to the subject by a clinician and takes approximately 8 minutes to complete, as reported in [Table 7](#).

Mini-Mental State Exam (MMSE)²⁵

The MMSE is a brief, 30-point questionnaire that provides a quantitative measure of cognitive status in adults and is widely used to screen for cognitive impairment and to estimate the severity of cognitive impairment at a given point in time. The MMSE total score ranges from 0 to 30, with lower score indicating greater impairment. The subject must have a score of greater than 15, inclusive, at screening to be eligible for study participation. It is administered to the subject by a trained rater and takes approximately 10 – 15 minutes to complete, as reported in [Table 7](#).

Columbia-Suicide Severity Rating Scale (C-SSRS)²⁶

The C-SSRS is a systematically administered instrument developed to track suicidal adverse events across a treatment study. The instrument is designed to assess suicidal behavior and ideation, track and assess all suicidal events, as well as the lethality of attempts. Additional features assessed include frequency, duration, controllability, reason for ideation, and deterrents. The C-SSRS is considered a low-burden instrument as it takes less than 5 minutes to administer. It is administered to the subject by a clinician and takes less than 5 minutes to complete, as reported in [Table 7](#).

Any subject noted to have suicidal ideation with plan within the prior month, either via answering "yes" to questions 4 or 5 to the suicidal ideation portion of the C-SSRS or via clinical interview, will be evaluated immediately by the study physician. The AbbVie Medical Director will also be informed. Appropriate steps will be taken to protect the subject, including but not limited to possible discontinuation from the study and referral for appropriate psychiatric care. Any such subject at screening or on Day 1 will also be excluded from the study.

5.3.1.2 Collection and Handling of Biomarker and Pharmacogenetic Research Samples

Biomarker Samples

Blood and CSF samples will be collected as outlined in the Study Activities Table ([Appendix C](#)) and may be utilized to evaluate known and/or novel disease-related or drug-related biomarkers. The biomarker rationale will be discussed in the Biomarker Research Variables Section (Section [5.3.6.1](#)).

All biomarker samples should be collected, processed, labeled and shipped as outlined in the study-specific laboratory manual, which will be provided separately.

AbbVie (or people or companies working with AbbVie) will store the samples in a secure storage space with adequate measures to protect confidentiality. The samples may be retained while research on ABBV-8E12, or drugs of this class, or PSP continues, but for no longer than 20 years from the end of the study, or per local requirement.

Blood samples (approximately 11 mL) will be collected prior to the start of the infusion (0 hour, no more than 30 minutes prior to the start of the infusion) at the time points indicated in the Study Activities Table ([Appendix C](#)). Blood samples collected at Week 52 (Study Completion/Premature Discontinuation Visit) may be collected at any time during that visit.

CSF samples (18 – 20 mL) will be collected by lumbar puncture.

MAPT Pharmacogenetic Sample

One (required) 4 mL whole blood sample will be collected from each subject at study Day 1 for microtubule associated protein tau (MAPT) haplotype and progranulin (GRN) pharmacogenetic analysis. This sample will not be used for any testing other than MAPT haplotyping and genetic analysis of GRN mutations.

Optional Pharmacogenetic Exploratory Research Samples

Subjects will have the option to provide samples for exploratory research. Subjects may still participate in the main study even if they decide not to participate in this optional exploratory research.

AbbVie (or people or companies working with AbbVie) will store the exploratory research samples in a secure storage space with adequate measures to protect confidentiality. The samples will be retained while research on ABBV-8E12 (or drugs of this class) or PSP and related conditions continues, but for no longer than 20 years after study completion. The procedure for obtaining and documenting informed consent for exploratory research samples is discussed in Section 9.3. Instructions for the preparation and shipment of the exploratory research samples will be provided in a laboratory manual.

Optional whole blood pharmacogenetic samples for Deoxyribonucleic Acid (DNA) and Ribonucleic acid (RNA) isolation will be collected from each subject who consents to provide samples for exploratory research. Optional whole blood samples (6.5 mL) for DNA and RNA isolation will be collected at the following time points:

- Day 1 (Dose 1)
- Day 85 (Dose 5)
- Week 36 (Dose 11)
- Week 52: (Completion/Premature Discontinuation Visit)

All pharmacogenetic samples (mandatory and optional) should be collected, processed, labeled and shipped as outlined in the study-specific laboratory manual, which will be provided separately.

5.3.1.3 Confinement

Subjects in Cohort J1 will be required to be confined for a minimum of 24 hours following their first dose. The Investigator will assess the subject for safety prior to discharge to determine that the subject can be discharged. If a subject is suspected of

having any abnormality during the medical examination prior to discharge, additional testing, including the extension of the confinement, will be considered.

5.3.1.4 Meals and Dietary Requirements

There are no dietary requirements or restrictions for this study.

5.3.2 Drug and Anti-Drug Antibody Concentration Measurements

5.3.2.1 Collection of Samples for Analysis

Specific instructions for collection of blood samples and subsequent preparation and storage of the serum samples for the pharmacokinetic assays of ABBV-8E12 will be provided by the central laboratory, the Sponsor, or its designee.

Blood Samples for ABBV-8E12 Assay

Blood samples, approximately 3 mL for ABBV-8E12 analysis will be collected by venipuncture as follows:

For Subjects Enrolled in Cohort 1 and Cohort J1 (*See Below for Allowable PK Windows)

- **Day 1 (Dose 1)**
 - Prior to the start of the infusion (0 hour, no more than 30 minutes prior to the start of the infusion), immediately after the end of the infusion (within 15 minutes) and 1 and 2 hours after the end of the infusion.
- **Day 5**
 - Sample may be collected at any time during the visit.
- **Day 15 (Dose 2)**
 - Prior to the start of the infusion (0 hour, no more than 30 minutes prior to the start of the infusion), immediately after the end of the infusion (within 15 minutes) and 1 and 2 hours after the end of the infusion.
- **Days 29 and 57 (Doses 3 and 4)**
 - Sample may be collected at any time during the visit.

- **Day 85 (Dose 5)**
 - Prior to the start of the infusion (0 hour, no more than 30 minutes prior to the start of the infusion), immediately after the end of the infusion (within 15 minutes) and 1 and 2 hours after the end of the infusion.
- **Days 89 and 99**
 - Sample may be collected at any time during the visit.
- **Weeks 16, 24, and 36 (Doses 6, 8, and 11, respectively)**
 - Prior to the start of the infusion (0 hour, no more than 30 minutes prior to the start of the infusion).
- **Week 52 (Study Completion/Premature Discontinuation Visit)**
 - Sample may be collected anytime during the day.
- **Weeks 60 and 68 (Post-Treatment Follow-up Period)**
 - Sample may be collected anytime during the day.

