***Cohort 1 and Cohort J1 Allowable PK Windows**

On Days 1, 15, and 85 and at Weeks 16, 24, and 36, the PK samples collected prior to infusion should be collected within 30 minutes of the start of infusion. For 1-hour post-dose samples (Days 1, 15, and 85), the allowable PK window is ± 6 minutes, and for 2-hour post-dose samples (Days 1, 15, and 85), the allowable PK window is ± 12 minutes. The allowable window is ± 2 days for samples scheduled on Days 5, 89, and 99, and ± 4 days for samples scheduled on other study days.

For Subjects Enrolled in Cohort 2 (*See Below for Allowable PK Windows)

- **Days 1, 29, 85, and Weeks 24 and 36 (Doses 1, 3, 5, 8, and 11, respectively)**
 - Prior to the start of the infusion (0 hour, no more than 30 minutes prior to the start of the infusion).
- **Day 15 (Dose 2)**
 - Prior to the start of the infusion (0 hour, no more than 30 minutes prior to the start of the infusion), immediately after the end of the infusion (within 15 minutes) and 1 and 2 hours after the end of the infusion.

- **Week 52: (Study Completion/Premature Discontinuation Visit)**
 - Sample may be collected anytime during the day.
- **Weeks 60 and 68 (Post-Treatment Follow-up Period)**
 - Sample may be collected anytime during the day.

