***Cohort 2 Allowable PK Windows**

On Days 1, 15, 29, and 85 and at Weeks 24 and 36, the PK samples collected prior to infusion should be collected within 30 minutes of the start of infusion. For 1-hour post-dose sample (Day 15), the allowable PK window is ± 6 minutes, and for 2-hour post-dose samples (Day 15), the allowable PK window is ± 12 minutes. For the samples scheduled for Weeks 52, 60, and 68, the allowable window is ± 4 days.

Blood Samples for ABBV-8E12 Anti-Drug Antibodies (ADA) Assays

Blood samples, approximately 3 mL for ABBV-8E12 ADA analysis will be collected by venipuncture. The collection schedule for ADA will be the same for subjects who previously did or did not participate in the Single-Ascending Dose Study (Study C₂N-8E12-WW-104). The schedule for ABBV-8E12 ADA collection is as follows:

For Subjects Enrolled in Cohort 1 and Cohort J1 (*See Below for Allowable ADA Windows)

- **Days 1, 15, 29, 57, 85, and Weeks 16, 24, and 36 (Doses 1, 2, 3, 4, 5, 6, 8, and 11, respectively)**
 - Prior to the start of the infusion (0 hour, no more than 30 minutes prior to the start of the infusion).
- **Days 89 and 99**
 - Sample may be collected anytime during the day.
- **Week 52: (Study Completion/Premature Discontinuation Visit)**
 - Sample may be collected anytime during the day.
- **Weeks 60 and 68: Post-Treatment Follow-up Period**

- Sample may be collected anytime during the day.

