5.3.5 Pharmacokinetic Variables

Values for the following pharmacokinetic parameters will be estimated using non-compartmental methods: maximum observed serum concentration (C_{max}), the time to C_{max} (peak time, T_{max}), the area under the concentration time curve (AUC) over the dosing interval after the first and the fifth doses in Cohort 1 and Cohort J1; and the observed serum concentration at the end of a dose interval (C_{trough} , concentration prior to infusion on a day of dosing) in both Cohort 1, Cohort J1, and Cohort 2.

The concentration of ABBV-8E12 in CSF will be summarized after the fifth dose and after the final dose if administered at least 3 months after the previous LP for subjects in Cohort 1 and Cohort J1, and after final dose for subjects in Cohort 2.

A mixed-effect modeling approach will be used to estimate the population central value and the empirical Bayesian estimates of the individual values for ABBV-8E12 clearance (CL) and volume of distribution (V).

Additional parameters may be calculated if useful in the interpretation of the data.

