For the first dose interval, the concentration at the beginning of infusion of the dose will be assumed to be 0 even if the scheduled pre-dose blood sample is mistakenly obtained after the beginning of infusion. For the fifth dose interval, the concentration of the pre-dose sample will be used as the concentration at the beginning of infusion of the dose provided that the blood sample is obtained in the 30 minute interval before the beginning of infusion. If the blood sample is obtained earlier than 30 minutes before the beginning of infusion, for the calculation of AUC the concentration at the beginning of infusion will be the $C_{obs} \times e^{-\beta t}$, where C_{obs} is the reported measurement for the pre-dose concentration, β is the rate constant determined from the exponential curve defined by the last two concentrations in the fifth dose interval and t the length of the time interval between the pre-dose blood sample and the beginning of infusion. If the pre-dose sample for the fifth dose interval is mistakenly obtained after the beginning of infusion of the dose, a value for the concentration at the beginning of the dose interval (beginning of infusion) must be imputed unless the sample was obtained within a very few minutes of the beginning of infusion (< 15 minutes). The data of other subjects in the same treatment group who have values for the concentrations at the beginning of the fifth dose interval, the beginning of the fourth dose interval and the end of the fifth dose interval may be used to obtain a linear regression model for the concentration at the beginning of the fifth dose

interval, with the concentrations at the beginning of the fourth dose interval and the end of the fifth dose interval as explanatory (predictor) variables. The missing value may be replaced by the predicted value from the regression model.

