12.3 Model and Tests

Unless stated otherwise, hypothesis tests will be performed at significance level 0.050.

Change in Concentration with Repeated Dosing

The concentration data of the planned pre-infusion sampling times of Cohort 2 (Days 15, 29 and 85 plus Weeks 24 and 36) will be analyzed to investigate change in serum concentration over time. The data of Cohort 1 and Cohort J1 will also be included in this analysis except for Day 29. The logarithmic transformation will be used unless the data show that the logarithm has substantial non-symmetry (e.g., magnitude of skewness coefficient > 1.0) while untransformed concentration or another transformation has an approximately symmetric distribution. A MMRM analysis will be performed. The model

will have fixed effects for dose level, geographical region (as identified in Section 10.7), classification by time, interaction of dose level and time and the interaction of region and time. The subjects will be viewed as a random sample, and an appropriate structure will be selected for the covariance matrix of the observations from a subject. If the statistic on the interaction of region and time is not significant at level 0.050, that term will be removed from the model. The concentration central value estimate versus time curves for the two dose levels will be plotted on the same graph, with the estimate of the central value for a dose level at a given time being the back transformation of the SAS least squares mean for the transformed data.

Dose Proportionality

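### In Cohorts 1 and J1 the Day 29 and Day 57 PK samples are not tied to the pre-infusion time, so up to about 52 troughs are not assured, and the concentration summaries and one SAP imputation rule do not allow for this

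*Protocol*

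**What the plan says.** **Sampling.** For Cohorts 1 and J1, Protocol Section 5.3.2.1 gives one PK timing rule for the visits of the third and fourth infusions (Days 29 and 57): "Sample may be collected at any time during the visit". The window paragraph for these cohorts agrees, since its list of pre-infusion samples omits both days: "On Days 1, 15, and 85 and at Weeks 16, 24, and 36, the PK samples collected prior to infusion". Protocol Table 4 agrees too: on these days the ADA entries carry the pre-infusion footnote and the PK entries do not.

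**Neighbouring rules.** In the same section, the ADA schedule for these cohorts requires a draw in the half hour before infusion on both days. Cohort 2 gives a pre-infusion PK sample on Day 29 and none on Day 57. Protocol Section 5.3.5 defines the trough, for every cohort, as the "concentration prior to infusion on a day of dosing".

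**Analysis.**
- SAP Section 12.3, matching Protocol Section 8.1.7.2, restricts the repeated-dosing MMRM: "The data of Cohort 1 and Cohort J1 will also be included in this analysis except for Day 29". The protocol synopsis lists Day 29 among the pre-infusion times for that model without this exception.
- Protocol Section 8.1.7.1 and SAP Section 12.2 summarise serum concentrations at each scheduled sampling time by dose level. Neither distinguishes samples taken before infusion from those taken after.
- SAP Section 12.1 deals with a Dose 5 pre-dose sample taken by mistake after the infusion has begun. Other subjects' concentrations at the start of the fifth interval, "the beginning of the fourth dose interval and the end of the fifth dose interval may be used to obtain a linear regression model". The fourth dose interval starts on Day 57.

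**The concern.** A sample drawn at any point of an infusion visit may be a trough, a value close to the peak, or something in between. These two cohorts were set up for augmented PK assessment, yet on Day 29 they have a looser rule than Cohort 2, and the documents give no reason.

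Three things are at stake:

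1. **Summaries.** The Day 29 and Day 57 concentration summaries may mix troughs with post-infusion values and then describe neither. On Day 57 no cohort has an assured trough.
2. **Imputation.** The regression in SAP Section 12.1 needs a concentration from the start of the fourth interval. A post-infusion Day 57 value used in that role would be the wrong quantity.
3. **Avoidable loss.** Day 29 troughs that could have entered the MMRM are set aside, although blood is already drawn before infusion at that visit.

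PK is a secondary objective, so this bears on the quality of a planned description. It does not bear on the efficacy comparison.

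**Working it through.** **Counts.** Inputs are the cohort sizes in Protocol Table 1 and the 1:1:1 allocation in Protocol Section 5.1.

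- Plan's own totals: 30 + 9 = 39 in Cohorts 1 and J1; 30 + 9 + 276 + 15 = 330 overall. Both reproduce.
- Active drug, Cohorts 1 and J1: 39 × 2/3 = 26 (Japan 9 × 2/3 = 6).
- Active drug, Cohort 2: (276 + 15) × 2/3 = 194. All cohorts: 330 × 2/3 = 220.
- Troughs not assured: 26 × 2 = 52.

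**MMRM.** The model has five times (Days 15, 29 and 85, Weeks 24 and 36).

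- Planned active observations: 5 × 220 = 1,100. Excluded: 26, and 26/1,100 = 2.4%.
- Cohorts 1 and J1 keep four of the five times.
- If all 26 Day 29 values were pre-infusion, Day 29 would rise from 194 to 220 troughs (+13%). √(220/194) = 1.065, so the cross-sectional standard error would fall by about 6%.

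These figures are before dropout.

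**How far a post-infusion value sits from a trough.** Assumptions: one compartment, equal bolus doses on Days 1, 15, 29 and 57, and the 27 to 37 day half-life in the Protocol Introduction. In units of one dose's immediate increment, the trough on day D is the sum over earlier doses of 2^(−(D − dose day)/half-life), and r = (trough + 1)/trough.

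| Day | Half-life (days) | Trough | r |
|---|---|---|---|
| 29 | 27 | 0.487 + 0.698 = 1.185 | 1.84 |
| 29 | 37 | 0.592 + 0.769 = 1.361 | 1.74 |
| 57 | 27 | 0.237 + 0.340 + 0.487 = 1.065 | 1.94 |
| 57 | 37 | 0.350 + 0.455 + 0.592 = 1.397 | 1.72 |

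**Effect on the arithmetic means.** The documents do not say what share f of the samples is post-infusion, so a range is shown. Within Cohorts 1 and J1 the mean exceeds the trough mean by f(r − 1). In the Day 29 pool of all active subjects it exceeds it by f(r − 1) × 26/220, assuming equal true troughs across cohorts.

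| f | Day 29, Cohorts 1 and J1 | Day 29, all active | Day 57, Cohorts 1 and J1 |
|---|---|---|---|
| 0.25 | 18 to 21% | 2.2 to 2.5% | 18 to 23% |
| 0.5 | 37 to 42% | 4.3 to 5.0% | 36 to 47% |
| 1 | 73 to 84% | 8.7 to 10.0% | 72 to 94% |

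The pooled Day 29 mean moves modestly. The cohort-level Day 29 and Day 57 means could move a lot. The model ignores distribution and infusion time, so these figures are for scale only.

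**The case against.** The case for leaving the plan alone has real substance.

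- **It is consistent.** The sampling text, the windows, Table 4 and the MMRM exclusion all treat these as samples without trough status. That looks deliberate. It stands as a defence of the MMRM, but not of the summaries, which have no matching exclusion.
- **The main PK analyses do not need these samples.** AUC and Cmax are planned for the first and fifth dose intervals. Dose proportionality uses those intervals and the Week 16 trough. This stands.
- **The imputation is remote.** It arises only when the Dose 5 pre-dose sample is taken 15 minutes or more after infusion start, the regression is optional, and SAP Section 12.4 limits imputation to suitable subjects. A careful analyst would not treat a post-infusion sample as a start-of-interval value. This largely stands; what remains is that no timing condition is written down.
- **Population PK uses actual sampling times**, so these samples keep their value there. True, but the protocol says an analysis of this study alone may not be conducted, and SAP Section 3.0 places it outside the SAP.
- **It may be too late to change sampling.** SAP Section 12.3 already states that Cohorts 1 and J1 have no data from Canada, Europe or Australia, which suggests that both had enrolled. This stands and moves the weight of the fix to the SAP.

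A reader might infer that the troughs of these cohorts are unusable, that 52 troughs are lost, or that the Japanese intensive cohort has no usable trough between Days 15 and 85. The documents do not support this. Only two visits are affected, and a sample drawn before infusion is a valid trough whatever the rule allowed. Nor do the documents state that following trough build-up on these two days in these cohorts is a purpose of the Day 15 dose; Protocol Section 5.1 ties that dose to rapid steady state and the chance of showing a treatment effect.

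**Conclusion.** The point holds as a limited, avoidable gap. Up to about 52 troughs in about 26 active subjects are not assured to be pre-infusion; the number actually affected depends on when sites drew the blood, which the documents do not show. Troughs on Days 15 and 85 and at Weeks 16, 24 and 36 are secured by the protocol.

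The MMRM is protected by its exclusion. Two places are not: the summaries for Days 29 and 57, and the Day 57 predictor in SAP Section 12.1. The synopsis also disagrees with Protocol Section 8.1.7.2 and SAP Section 12.3 over Day 29.

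No primary, key secondary or safety conclusion is affected, and the documents do not support calling the accumulation analysis invalid. The counts assume exact 1:1:1 allocation within the cohorts and no dropout. The 1.7 to 1.9 ratio rests on the simple model above. The change is worth making because it costs almost nothing.

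**What to change.** **For any Cohort 1 or J1 subject still to be sampled:** in Protocol Section 5.3.2.1, take the Day 29 and Day 57 PK sample together with the existing pre-infusion ADA sample. Add both days to the pre-infusion list in the PK window paragraph, and put the pre-infusion footnote on those PK entries in Table 4.

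**For samples already drawn, in the SAP:**

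1. Classify each Cohort 1 and J1 Day 29 and Day 57 sample as pre- or post-infusion from its recorded time and the infusion start and stop times.
2. In Section 12.2, summarise the two classes separately.
3. In Section 12.3, admit confirmed pre-infusion Day 29 values to the MMRM in place of the blanket exclusion.
4. In Section 12.1, restrict the Day 57 predictor to confirmed pre-infusion samples.

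Reconcile the synopsis with whichever Day 29 rule is kept.

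**Cost:** wording and one derived variable, with no extra visit or sample. Protocol Section 5.5.1 has infusion times recorded to the minute. Sample clock times are implied by the use of actual times in SAP Section 12.1 and in the population PK plan; confirm that they were captured on these two days. The gain is up to 26 more Day 29 troughs (194 to at most 220), up to about 26 confirmed Day 57 troughs where none is now assured, and summaries that can be interpreted.
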